Clinimark [name]	TITLE: Respiratory Rate Verification Study – Gabi SmartCare Gabi Band Study ID# PR 2022-495 Principal Investigator: [name] Site ID # 001	DOCUMENT NUMBER PR# 2022-495 SHEET 2 of 28	REV 1
---	---	---	-----------------

Clinimark Statements

Confidentiality

The information contained in this document is confidential and is intended for the use of clinical investigators. It will not be copied by or distributed to persons not involved in the clinical investigations of Gabi SmartCare, unless such persons are bound by a confidentiality agreement with Clinimark or Gabi SmartCare.

Impartiality

Clinimark is committed to maintaining impartiality of laboratory and study activities. Personnel are trained on processes and protocols are followed to ensure conformity of the activities. Commercial, financial and other pressures are not allowed to compromise the impartiality of laboratory activities. This includes those risks that arise from lab activities, lab relationships, or from the relationships of its personnel.

The risk of Impartiality is mitigated by conducting this study according to the mutually agreed upon protocol, contractual arrangements, and standards or guidance documents if applicable.

Glossary

- **CIP** - Clinical Investigation Plan
- **FDA** – Food and Drug Administration
- **IRB** – Independent Review Board
- **ISO** – the International Organization for Standardization
- **NIST** – National Institute of Standards and Technology, **NIST** is the federal technology agency that works with industry to develop and apply technology, measurements, and standards.
- **Reference** – established accuracy used for clinical evaluations of other instruments
- **Device Under Test (DUT)** – the device being clinically evaluated
- **NSR** – Non Significant Risk
- **PPG** - Photoplethysmography
- **bpm** – beats per minute, in regards to heart or pulse rate
- **BPM** – Breaths per minute, in regards to respiratory rate
- **EtCO₂** – End Tidal Carbon Dioxide
- **RR** – Respiration/Respiratory Rate
- **PR** – Pulse Rate
- **ROI** – Region of Interest
- **A_{RMS}** - Accuracy Root Mean Square

$$A_{RMS} = \sqrt{\frac{\sum_{i=1}^n (DUT_i - Ref_i)^2}{n}}$$

Where:

- A_{RMS} is the accuracy root mean square.
- DUT is the test device during sample i.
- Ref is the Reference Respiratory Rate (EtCO₂) during sample i.
- n is the number of points.

Clinimark [name]	TITLE: Respiratory Rate Verification Study – Gabi SmartCare Gabi Band Study ID# PR 2022-495 Principal Investigator: [name] Site ID # 001	DOCUMENT NUMBER PR# 2022-495 SHEET 3 of 28	REV 1
---	--	---	-----------------

Respiratory Rate Verification Study - Gabi SmartCare Gabi Band

PR 2022-495

Summary

Objectives of the Clinical Investigation Plan

The purpose of this study is to conduct a Respiratory Rate accuracy Verification comparing the Gabi SmartCare Gabi Band to the Reference, an FDA cleared End Tidal Carbon Dioxide monitor (GE Datex-Ohmeda).

The testing will be conducted in order to obtain a full data set for Verification on a minimum of 23 participants. Multiple developmental phases may be conducted and will be reviewed for readiness for continuation to Verification. If modifications are warranted, the initial data sets will be used for algorithm development. The study will be split up into two phases:

- Phase I with a minimum of 8 subjects
- Phase II with a minimum of 15 subjects

Background

Respiratory Rate is an important physiological measurement in the healthcare setting. The gold standard in Respiratory Rate is based off of an airway measurement using end tidal carbon dioxide (EtCO₂) respiratory rate.

The medical device studied under this protocol will be the non-invasive and investigational Gabi SmartCare Gabi Band. All appropriate preliminary testing on the Gabi SmartCare Gabi Band has been successfully performed and demonstrates safety and efficacy for use in human studies prior to Clinimark's receipt of the devices. Gabi SmartCare Gabi Band is a non-invasive device that allows for real-time, remote monitoring using a sensor applied on the participant's upper arm.

Protocol Overview

After IRB approval, a minimum of 23 volunteer test participants will be enrolled for the verification study population. A maximum of 60 participants will be enrolled. An attempt will be made to include 3 darkly pigmented participants or 15% of the participant pool (whichever is larger). Participants will be from 0-5 years of age with the following distribution:

Population	Age Population	Requirement
Neonates	0-28 days	No requirement
Infant	>1 month – 24 months	Minimum 30% of participants
Pediatrics	>2 years – 5 years	Minimum 30% of participants

Each participant is expected to take 1-2 hours, including paperwork, sensor application, and a maximum of 60 minutes of data collection. Each participant will be connected to a commonly used End Tidal Carbon Dioxide monitor (GE Datex-Ohmeda) and the Gabi SmartCare Gabi Band. The end tidal carbon dioxide (EtCO₂) monitor will determine performance of respiratory rate metrics (GE Healthcare S5 Compact Monitor with M-COVX (K001814) or E-CaiO (K051092) modules). Each participant will be instrumented with neonatal or pediatric nasal cannula that allows for measurement of the EtCO₂. SpO₂ sensors may be placed on the feet and/or toes for safety monitoring purposes.

Data will be simultaneously and continuously recorded from the Reference EtCO₂ monitor and the Device Under Test (DUT). Periods of quiet will be encouraged. Data will be marked for stable quiet periods that are useable for analysis. There is no additional follow-up required for the investigation.

One minute epochs will be generated from the stable data periods for analysis. For verification, the Reference EtCO₂ waveform will be scored by counting the respiratory peaks per minute (See Appendix B: Sample Waveform

Clinimark [name]	TITLE: Respiratory Rate Verification Study – Gabi SmartCare Gabi Band Study ID# PR 2022-495 Principal Investigator: [name] Site ID # 001	DOCUMENT NUMBER PR# 2022-495 SHEET 4 of 28	REV 1
---	--	---	-----------------

Scoring Form for an example). The reviewers counting the raw EtCO₂ waveform will be blinded to the results from the test device. The DUT data will be averaged over the corresponding one minute period. The Accuracy root-mean-square (A_{rms}) will be the basis for evaluation and acceptance.

To 'Pass' this test the Gabi SmartCare Gabi Band (Device Under Test) must demonstrate an Accuracy root-mean-square (A_{rms}) of ≤3.0 breaths per minute when compared to the Reference EtCO₂ monitor.

Study Population

The study population will include a minimum of 23 neonates, infants, and pediatrics from 0-12 years of age. A maximum of 60 participants will be enrolled. The participant selection will be an equitable distribution of males and females of any race with varying skin tones. An attempt will be made to include 3 darkly pigmented participants (Fitzpatrick 5 or 6) or 15% of the participant pool (whichever is larger).

The parents or guardian of the participants must understand the study and consent to their child's participation in the study by signing the Informed Consent Form. Subjects 7 to 12 years of age will be provided an Assent. The study will be explained within his/her ability to understand. Participant enrollment and participation in this clinical study is based on meeting the inclusion criteria and none of the exclusion criteria, a satisfactory screening, and the participant and data demographics needed for the study.

Inclusion Criteria

- Ability of the parent or guardian to understand and provide written informed consent
- Participant is 0 to 12 years of age
- Subjects that are between 7 and 12 years of age must provide Assent to participate in the study

Population Criteria to be Included

- A minimum of 30% of participants will be >1 month to 24 months old
- A minimum of 30% of participants will be >2 years to 12 year

Exclusion Criteria

- Participants evaluated by the Investigator and Clinical Staff and found to be medically unsuitable or have self-reported health conditions that are currently unstable as identified in the Participant Demographics and Screening Record Form
- Participant has injuries, deformities or abnormalities that may prevent proper application of the device under test
- Participants with severe contact allergies to standard adhesives, latex or other materials found in pulse oximetry sensors, ECG electrodes, or other medical sensors (self-reported)

It is expected that the data collection will take two days for Phase I and four days for Phase II. There is no additional follow-up required for the investigation.

Clinimark [name]	TITLE: Respiratory Rate Verification Study – Gabi SmartCare Gabi Band Study ID# PR 2022-495 Principal Investigator: [name] Site ID # 001	DOCUMENT NUMBER PR# 2022-495 SHEET 5 of 28	REV 1
---	---	---	-----------------

Respiratory Rate Verification Study – Gabi SmartCare Gabi Band

PR 2022-495

Table of Contents

Clinimark Statements.....	3
Glossary	3
Summary.....	4
Objectives of the Clinical Investigation Plan	4
Background	4
Protocol Overview	4
Study Population.....	5
Inclusion Criteria	5
Population Criteria to be Included.....	5
Exclusion Criteria	5
Table of Contents.....	6
Objectives of the Clinical Investigation Plan	9
Identification and Description of the Investigational Device.....	9
Data Acquisition System for the Investigational Device	10

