- Study Stopped due to Technical Problems
- Study may be stopped due to Protocol Deviation
- Study Terminated by Sponsor
- Study Stopped due to Adverse Event

Any data collected to the point of a decision to terminate the study will be reviewed for inclusion to the analysis prior to generation of the final results. Data excluded from the analysis will be documented with justifications for the Verification of the product. During the development phase, usage and removal of the data is at the sponsors discretion.

Procedure

1. Complete equipment setup and checkout prior to starting study.
2. Set and / or synchronize the computer clocks for the sponsor and Clinimark data collection systems
3. Explain the procedure to the participant's parent or guardian. Have them read the Informed Consent Form and review the information, answering all questions. Once all questions have been answered, have the parent or guardian sign the form. Have the parent or guardian complete the Participant Demographics and Screening Record Form and verbally question the parent or guardian about the health history. Each parent or guardian will be asked if they want a copy of the consent form prior to release.
 - a. Participants ranging in age 7–12 years will additionally go through an Assent process.
4. Based on the responses to the Participant Demographics and Screening Record Form and health assessment, record accepted or declined from the study. Continue if accepted into the study.
5. Position participant in the parent's lap, on bed, or in a chair (for pediatric participants).

Clinimark [name]	TITLE: Respiratory Rate Verification Study – Gabi SmartCare Gabi Band Study ID# PR 2022-495 Principal Investigator: [name] Site ID # 001	DOCUMENT NUMBER PR# 2022-495 SHEET 14 of 28	REV 1
---	---	--	-----------------

6. Setup and verify communication between the devices and data collection systems.
7. Record device information for tracking (manufacturer, model #, serial/lot, hardware/software control info).
8. Record participant information, participant number, and demographics information.
9. Apply a SpO₂ sensor to the participant following the IFU for the pulse oximeter.
 - a. Sensors may be placed on the feet or hands.
 - b. Supplemental tape may be used to secure the sensors on feet that are too large for the sensor bandage length.

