10. Apply the nasal cannula to the participant. Use neonatal/infant soft tape as necessary to adhere the nasal cannula.
11. Apply Device Under Test sensors to the participant per the IFU. Adjust sensors and devices as appropriate, ensuring the Device Under Test is producing valid outputs, and record the placement on test form.
12. Allow readings to stabilize for at least a few minutes.
13. Begin Respiratory Rate evaluation.
 - a. Start data collection and elapsed timer display.
 - b. Encourage the participant to be quiet.
 - c. Mark in MediCollector quiet periods with minimal movement, talking, and/or crying. Note motion events, location, position, and activity level of the participant in the CRF.
 - d. Data from the Reference (EtCO₂ waveform) and the DUT will be recorded continuously. Additional study notes that describe conditions of the test as well as deviations, device issues, and any adverse events will be recorded in written documentation.
 - e. Record data for up to 60 minutes.
14. Remove all sensors and end the data collection.
15. The clinician will review any final questions with the parent or guardian and assess any effects from the study. The participant will be released with no further follow up required.

Statistical Analysis

Clinimark will perform the statistical analysis for the verification phase.

The Reference Respiratory Rate based on EtCO₂ will be collected simultaneous to the Device Under Test Respiratory Rate during one minute epochs during quiet, stable periods. The data will be paired based on syncing of the data collection system clocks. During the stable data sets, the DUT data will be averaged in approximately 60 second intervals. The Reference EtCO₂ waveform will be scored by counting the respiratory peaks per minute (See Appendix B: Sample Waveform Scoring Form for an example). The reviewers counting the raw EtCO₂ waveform will be blinded to the results from the test device.

The final pairing to be analyzed is Reference EtCO₂ scored and counted waveform with the average of the simultaneous 60 second period for the DUT. The Accuracy root-mean-square (A_{rms}) will be the basis for evaluation and acceptance.

Endpoint / Comparator

The primary objective of this study is to compare the accuracy of the device under test for the measurement of respiratory rate to the Reference, which is an End Tidal Carbon Dioxide Monitor (EtCO₂). For verification, the EtCO₂ waveform will be scored by counting the respiratory peaks per minute.

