The endpoint of interest is accuracy as measured by the Accuracy root-mean-square (A_{rms}) difference between the Device Under Test (DUT) and the Reference Respiratory Rate as counted by EtCO₂ scored waveform (Ref) for all stable respiratory periods where

Clinimark [name]	TITLE: Respiratory Rate Verification Study – Gabi SmartCare Gabi Band Study ID# PR 2022-495 Principal Investigator: [name] Site ID # 001	DOCUMENT NUMBER PR# 2022-495 SHEET 15 of 28	REV 1
--	--	---	----------

$$A_{rms} = \sqrt{\frac{\sum(DUT - Ref)^2}{n}}$$

Mean bias will also be generated:

$$Bias = \frac{1}{n} \sum_{i=1}^n (DUT_i - Ref_i)$$

Acceptance Criteria: Passing requires an A_{rms} of ≤ 3.0 cpm.

Sample Size Justification

This study will utilize a sample size of 20 participants with 7 to 11 usable data points per participant, providing ≥ 200 data points over the specified breath per minute range.

Success for this study is defined as $A_{rms} \leq 3$ cpm. The A_{rms} statistic measures accuracy of a device under test (DUT) when compared to a reference device (REF) over a range of values. Accuracy, measured by the A_{rms} statistic, can be affected by both random and systematic components of error. Here we estimate power to obtain an $A_{rms} \leq 3$ cpm for this study through simulation using parameters estimated from two preliminary studies conducted previously by Clinimark. Respiratory rate study 1 composed of 894 data points from 18 study participants. respiratory rate study 2 composed of 913 data points from 20 study participants. Both studies had respiratory rate targets of 5, 10, 15, 20, 25, 30, 35, 40 and 45 breaths per minute. The A_{rms} statistics are 2.8 cpm and 1.2 cpm for Study 1 and Study 2 respectively. For more information about the results and standard respiratory rate metrics please refer to 'Summary of Respiratory Rate Data and Results from Clinimark Studies' dated May 1, 2019. These preliminary data contain the features of real data, such as within participant correlation that is present due to repeated measurements on the same study participants. Note this sample size was conducted on studies with adult populations where paced breathing can be used to get a range of repository rates. Participants in this study will breathe at their natural rate.

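### Blinding is stated only for the waveform counters; the protocol does not say that epoch cutting and the inclusion review are done without sight of device values

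*Protocol*

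**What the plan says.** **Blinding.** Protocol Overview, Method, Statistical Analysis and Appendix B all carry the same statement: "The reviewers counting the raw EtCO₂ waveform will be blinded to the results from the test device". No other step in the protocol or SAP is described as blinded.

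**Which minutes are analysed.** Three steps decide this.
- Marking. Protocol Overview and Method say "Data will be marked for stable quiet periods that are useable for analysis". Procedure step 13c reads "Mark in MediCollector quiet periods with minimal movement, talking, and/or crying". This is done during the session, in the software that records the reference.
- Epoch cutting. Protocol Overview and Method say "One minute epochs will be generated from the stable data periods for analysis". They name no role, start rule, number of epochs or numeric definition of stability.
- Inclusion review. Under Criteria for Study Termination, data collected up to a decision to terminate "will be reviewed for inclusion to the analysis prior to generation of the final results". Completion of the study is one of the listed termination conditions, so this can be read as covering the ordinary end of the study. The section adds: "Data excluded from the analysis will be documented with justifications for the Verification of the product". It gives no criteria for exclusion.

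**Endpoint and amount of data.** Endpoint / Comparator defines A_rms "for all stable respiratory periods". Procedure step 13e records up to 60 minutes per participant. Sample Size Justification expects 7 to 11 usable points per participant.

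**Who does what.** The testing organisation's staff collect the device data on a system separate from its automated collection system (Data Acquisition System for the Investigational Device). The same organisation performs the verification analysis (Statistical Analysis). The SAP has no rule for selecting or excluding epochs.

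**The concern.** A_rms averages squared differences, so a few large differences carry much of its value. Whoever decides that a minute was not stable, or should be excluded, can lower A_rms if the device-minus-reference difference is known at that moment. The protocol already accepts that knowing the device value can colour a judgement, since it blinds the counters. Choosing the minutes to be counted involves at least as much discretion.

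There is room for that discretion: 7 to 11 points from up to 60 recorded minutes is about 12% to 18% of the recording (7/60 and 11/60). Much of the remainder will be lost simply because young children move and cry, but the line between usable and unusable is not defined in numbers. At stake is the false-pass rate for a device whose true error lies just above the limit, and how well a genuine pass withstands challenge.

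**Working it through.** **Inputs.** From Protocol, Sample Size Justification: slope 0.97039, bias term −0.08434, between-participant variance 0.4724, within-participant variance 7.04, reference rates 5 to 45 in steps of 5, pass if A_rms ≤3.0. Assumed: 23 participants (the protocol minimum) × 9 epochs (the middle of 7 to 11) = 207 epochs. The true A_rms values and the number of epochs dropped are also assumptions. The documents give neither.

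**The plan's own figure.** Simulating the protocol's model, with the bias term as intercept and 10,000 runs, gives a pass rate of 79.8% for 27×9, 81.3% for 16×18, 80.8% for 11×27 and 81.9% for 10×36. The protocol claims more than 80% for each, so the model is reproduced.

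**Model for the check.** Difference = b + participant effect + residual.
- b = (0.97039 − 1) × 25 − 0.08434 = −0.82, taking the mean reference rate of 25 from the adult paced studies.
- Total variance = A² − b², where A is the true A_rms.
- Between-participant share = 0.4724 / (0.4724 + 7.04) = 0.063.
- Example for A = 3.1: 9.61 − 0.67 = 8.94, split into 0.56 between and 8.38 within.

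Each simulated trial was scored on all 207 epochs, and again after removing 4 of them (4/207 = 1.9%).

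| True A_rms | All epochs | Worst 4 removed | 4 at random from the worst 20 removed |
|---|---|---|---|
| 3.1 | 28% | 74% | 54% |
| 3.2 | 11% | 50% | 30% |
| 3.3 | 4% | 28–30% | 13% |

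Repeat runs differ by 1 to 2 points. Using b = −0.084 instead of −0.82 leaves the results almost unchanged. Removing 4 epochs chosen without regard to the error also leaves the pass rate unchanged (28% at 3.1), so the effect comes from informed selection and not from exclusion as such.

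**Analytic cross-check.** For normal errors with mean zero, dropping the largest fraction p multiplies A_rms by √[(1 − 2(zφ(z) + p/2)) / (1 − p)], with z the two-sided cut-off. At p = 0.02, z = 2.326 and φ(z) = 0.0267, so the factor is √[(1 − 2(0.062 + 0.010)) / 0.98] = 0.935. A true A_rms of 3.0/0.935 = 3.21 is therefore pulled to the limit.

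**Sensitivity (20 × 10 epochs, worst 4 removed, true A_rms 3.1 and 3.2).**
- Normal errors as above: 27% to 75%, and 12% to 52%.
- Heavy-tailed (t-distributed) errors: 40% to 94%, and 24% to 85%.
- Shared bias of 2.0 with equal variances: 40% to 62%, and 29% to 50%.

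**SAP rule (upper one-sided 95% bound below 3; subject-level bootstrap, 20 × 10).** True A_rms 3.0: 10% to 53%. True A_rms 3.1: 2% to 30%.

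**The case against.** The strongest reply is that silence is not exposure. A reader might infer that the people choosing epochs work with the device result in view. The documents do not say so. They do not say who cuts epochs or what that person sees, and device data are held on the tablet and uploaded for analysis only when collection stops. Live marking uses behavioural criteria in the reference software. That largely answers the concern for marking and leaves the steps after collection.

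A reader might also take Procedure step 11, "ensuring the Device Under Test is producing valid outputs", as evidence of access. It is a set-up check before stabilisation and recording, and shows nothing about anyone seeing device-minus-reference error.

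There are further safeguards. The endpoint covers all stable periods, so dropping a marked stable epoch would depart from its definition. Exclusions need documented justification. Original device files are preserved, with analysis in a separate file (Data and Quality Management / Confidentiality). Case report forms hold stability annotations and are signed and dated (Data Collection Forms / Case Report Forms). The sponsor's discretion to remove data is limited to the development phase.

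All of this stands, and it narrows the point. It does not remove it: a trail makes selection detectable afterwards, and the all-stable-periods wording binds only if stability is settled without device data.

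**Conclusion.** The gap is real and cheap to close. Blinding is stated for counting and for nothing else. For epoch cutting and the inclusion review, the documents give neither masking nor an objective rule. They do not show that these steps are unblinded or that any selection will occur.

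A further tempting inference is that losing about 2% of epochs turns a likely fail into a pass. That 2% is an assumption made here, and the figures are an upper bound. They require removal of exactly the largest errors and a device just over the limit. At a true A_rms of 3.2 the result is an even chance, and at 3.3 a fail remains likely. With imperfect selection at 3.2, or under the SAP's confidence-bound rule at 3.1, a fail also remains likely (about 30% pass in each case). Within those limits the effect on a borderline device is large: about 28% to 74% at 3.1 under the protocol's rule. This is a cheap improvement, not a defect that invalidates the design.

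**What to change.** Add one paragraph to Statistical Analysis, repeated or referenced in the SAP:
- Epoch boundaries and exclusions are set using only the EtCO₂ waveform, the MediCollector annotations and the case report form notes.
- A dated epoch list is frozen before device values are merged.
- The report gives the number of frozen epochs with no device output.
- If an epoch is removed after merging, A_rms is reported with and without it.

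The cost is that paragraph and one locked file. No change to data collection or staffing is needed. The one possible downside is a slightly less favourable A_rms.
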